Trial Design:	 Randomisation: Mixed-block 1:1 randomisation stratified by site and sex managed by Derby CTSU. Intervention: (See flow chart) The intervention group will use the AI enabled platform with the new AI module for 30 days after surgery in addition to standard post-operative wound follow-up care for 60 days after surgery. Participants will be asked to submit images and information every 7 days post operatively, up until 30 days. Participants can also submit an image during the 30 days whenever they have a concern. Control: The control group will receive standard post-operative wound follow-up care for 60 days after surgery. Standard care, mapped during the economic scoping exercise in WP6 may include; out-patient appointments, advised to contact GP, or no follow-up. Neither of the two participating sites use Isla as their standard care. Data collection: We will develop online surveys for patients and staff focusing on safety, acceptability, quality of life, and barriers to underserved groups. Interviews with staff/patients exploring issues raised in surveys. Purposive sampling to include a range of ages, sex, ethnicities, physical abilities/carer dependence and socioeconomic status. Other tools include platform review, medical notes review and patient telephone calls at 30 and 60 days.
Trial Participants:	Patients ≥18 years old having coronary artery bypass graft (CABG) surgery.
Planner Number of Sites:	2
Planned Sample Size:	120 - National data shows a wound problem rate of 21% with a cardiac wound infection rate of 8%. A sample size of 120 patients should provide around 12 patients in each group with a wound problem of which 4-5 patients should have a wound infection. This is sufficient to inform feasibility, safety and acceptability data. Wound problems identified by the Isla platform include Discolouration, unexpected fluids/tissue, sutures/clips observed, incision after 14 days.
Treatment Duration:	Participants in the intervention group will be enrolled on Isla at hospital discharge or at 5 days after surgery for patients not discharged by day 5 post op. Patients will receive text requests via Isla up to 30 days after surgery.
Follow Up Duration:	Duration of follow up: Wound monitoring follow up is for 30 days after surgery (as per national guidelines) and we will follow up all patients for 60
	days after surgery to capture readmissions and further surgery data.
Planned Start Date:	days after surgery to capture readmissions and further surgery data. As per IRAS form start date 1 st March 2024

Planned Study End Date:	Estimated Last Participant Last Visit (LPLV) – as per IRAS form study end date 28 th February 2025	
	Objectives	Outcome Measures
Primary:	To obtain safety outcomes data To obtain feasibility outcomes data To obtain acceptability outcomes data To obtain data for economic modelling	Safety outcomes Feasibility outcomes Acceptability outcomes Economic modelling outcomes
Investigational Device:	A new AI component (a wound prioritisation module) to an existing digital surgical wound monitoring platform. The new wound prioritisation module highlights images of surgical wounds which display signs of healing complication or infection. These images are then identified as requiring urgent priority review by a clinician for assessment rather than standard review.	
Eligibility Criteria:	Inclusion criteria: Patients having first/redo CABG surgeries with or without additional cardiac procedures such as valve replacement, patients with chest reopening during same admission as index surgery, patients with an existing non-infected wound complication, or any other infection except surgical site. Patients without a smartphone/with physical disability/with visual impairment will be eligible if their carer is able-bodied or has a smartphone.	
	Exclusion criteria : CABG requiring ve extracorporeal membrane oxygenat patients, or with a pre-existing surgi	ion (ECMO), ventilated or unconscious

FUNDING AND SUPPORT IN KIND

Funder(s)	Financial and Non-Financial Support Given NIHR i4i Call 24
NIHR i4i	Ref 204508

ROLES & RESPONSIBILITIES

Sponsor

The Sponsor, Guys and St Thomas' NHS Foundation Trust, take on overall responsibility for appropriate arrangements being in place for the set-up, management, conduct and reporting of the research project. The responsibility for management of this project has been delegated to Derby CTU, as outlined in the Collaboration Agreement, and in accordance with the Delegation of Responsibilities. The sponsor is not providing funds for this study but has taken on responsibility for ensuring finances are in place to support the research.

Funder

The study is funded by NIHR i4i

Study Management Committees

Trial Management Group

The trial management group will meet regularly to oversee the day-to-day management of the trial, including all aspects of the conduct of the trial. Any problems with study conduct and participating centres will be raised and addressed during TMG meetings.

Trial Steering Committee

The trial steering committee (TSC) will oversee and supervise the progress of the trial and ensure that it is being conducted according to the clinical investigation plan and the applicable regulations. The TSC will also review safety and data monitoring and quality. The TSC is an independent body that includes majority members who are not involved with the running of the trial.

Clinical Investigation Plan Contributors

A number of contributors have been involved in the development of the CIP, these include; the Chief Investigator, Joint-Lead, Statistician, Data Manager and Trial Manager, health economist, Industry partner (Islacare), and Sponsor's representative. Contributors are responsible for inputting into the design of the study, ensuring that it is designed transparently and efficiently.

Contents

[figure not shown]
SIGNATURE PAGE	3
KEY TRIAL CONTACTS	
TRIAL SUMMARY	-
FUNDING AND SUPPORT IN KIND	8
ROLES & RESPONSIBILITIES	9
LIST OF ABBREVIATIONS	12
STUDY FLOW CHART	13

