3.1 Secondary outcomes

Safety outcomes. More detailed discussion about reasons for compliance/non-compliance with the ISLA platform will be explored in the staff surveys and interviews and the patient intervention group surveys and interviews.

Feasibility outcomes: access/barriers to participation and willingness of participants to be randomised, and attrition rates, time and resources required to conduct assessments, number and severity of wound problems/infections, date of diagnosis.

Other secondary outcomes: number of photos received per patient, number of wound images/non wound images, number of quality images, number of requests (for images) complied with - intervention group only, number photos initiated by patients (intervention group only), number of follow-up requests.

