7.6 Trial Assessments

Procedures relating to the clinical investigation that patients will undergo.

Intervention group patients

Weekly requests to submit image and information about their surgical wound using their phone via the Isla wound monitoring platform. If no problem is identified patients are sent text confirming this, if a problem is identified patients will be contacted by clinicians to provide more information which may lead to treatment (note this aspect is not new and is already used in 8 cardiac centres in England).

Intervention	
Post surgery	Participant is sent SMS text requesting
day 7	wound image plus response to modified
	UKHSA SSI post-discharge questionnaire
Post surgery	Participant is sent SMS text requesting
day 14	wound image plus response to modified
	UKHSA SSI post-discharge questionnaire
Post surgery	Participant is sent SMS text requesting
day 21 (link	wound image plus response to modified
open until	UKHSA SSI post-discharge questionnaire
day 30)	

Both patient groups x1 online survey at 30 days (for all 120 patients – 15 mins each) x1 online interview at 30 days (for a subset of 10 patients from each group only, lasting around 40 mins)

x1 phone call at 30 days and also at 60 days to discuss any wound healing problems for all 120 patients lasting 15 mins

Staff

x1 online survey at 30 days for all surgeons and nurses who have been involved in using Isla – 15 mins

x1 online interview at 30 days for a subset of 10 staff who have been involved in using Isla -lasting around 40 mins

Online surveys will be hosted on Dacima and the interviews will be conducted via Teams and recorded using digital audio recording. The phone call to discuss the patients wound will use the post-discharge questionnaire from the UKHSA SSI surveillance programme. Qualitative data will be analysed and grouped into themes.⁷ Quantitative data will be analysed using simple descriptive statistics.

30 days has been chosen as the data collection point as this is the recommended follow-up time for a wound infection as stipulated by the national wound surveillance programme run by the UKHSA. Further data is collected at 60 days to identify any adverse events such as hospital re-admissions or further surgery the patients may have had.

We are interested to know if/how the following baseline characteristics influence patient engagement with digital wound monitoring- age, sex, location (*e.g.* rural/urban), socioeconomic status, English speaking.

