7.7 Qualitative assessments

Ten interviews with patients from each of the two groups and ten interviews with staff. The interviews will be semi structured, and the schedules will be developed based on relevant literature.³ The focus for the patients' interviews will be acceptability for the Isla platform, post-operative wound follow-up, and acceptability of taking part in the study. The staff interviews will focus on acceptability of the Isla platform and post-operative wound follow-up. The first two interviews will serve as a pilot and will be reviewed, and any amendments made to the interview schedule as required.

All interviews will take place via Microsoft Teams and will be digitally recorded with the permission of the participant. Interviews are expected to last around 40 minutes. Data from the interviews will be independently transcribed.

Interview data will be analysed using thematic content analysis.⁷

As the interviews will be remote, consent for the sub study will be conducted remotely. The research should take care to cover the Information leaflet and consent form with the participant on the recording, but only the researcher will sign the consent form. The recording of the participant giving consent will be audio recorded and transcribed.

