8.0 Name and Description of Investigational Device(s)

Isla is a remote surgical wound platform, which runs on all modern phones and tablets. Patients can use Isla to provide data (images and questionnaire responses) in response to pre-programmed text message requests. The new component under investigation is a module for the platform that uses artificial intelligence to identify 'red flags' on submitted wound images which are then prioritised for urgent review by clinicians. Examples of red flags are Discolouration, unexpected fluids/tissue, sutures/clips observed, incision

In this study, Isla will be offered to all adult patients (18 or over) having coronary artery bypass graft (CABG) surgery at the participating sites.. Isla is intended to capture information on surgical wounds remotely. The new AI module prioritises images with a concern for urgent review by a clinician. We plan to recruit 120 patients of which 60 will receive monitoring through Isla.

Isla is a digital platform. Isla sends patients text message requests for data about their wound. Patients can use their smart phone or ipad to take a photo of their wound which they send using their smart phone or email. They also provide responses to the modified UKHSA post discharge wound monitoring questionnaire.

Data is transferred securely using state-of-the art SHA256 encryption in transit and at rest. Standards include conformity with medical device regulations, General Data Protection Regulation (GDPR), NHS Digital Technologies Assessment Criteria (DTAC), the STARD-AI initiative and NICE Evidence Standards Framework for Digital Health.

Patients only use their own mobile or computing devices. There is no App to download. There is no physical contact with the Isla device. The Isla product is purely software.

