8.4 Assessment of Compliance

The Isla platform supports compliance:

- Monitoring: Patients will be sent automated requests as part of the pathway that they're on. Within the Isla platform users can view custom views for patients who have missed their requests or never responded to requests. This view will allow study teams to follow up non compliance to encourage to participate, understand non compliance and support patients through the process.
- As part of clinician and patient capture flows, a consent screen is presented to give the user or patient information about how and where data will be saved once uploaded to Isla. This gives the end user the opportunity to withhold consent at this point and not submit. Patients also have the ability to withhold consent from being contacted, and this will block further communication from the Isla platform
- Non compliance will be monitored, but won't result in patients being excluded from the study, as compliance is one of the things we are looking to measure to assess feasibility.

Compliance with assessment: The research nurse will document responses to patient phone calls at 30 days and 60 days to capture this data via Dacima for the online questionnaires/ surveys.

We want to document non-compliance as part of this feasibility study to inform a definitive study. Therefore, we will not withdraw any patients for non-compliance – with intervention, or with follow up assessment.

We are convening a participant advisory group to obtain feedback on how to improve recruitment and compliance.

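### Interviewees are not sampled on whether they submitted images and all interviews are by Teams, so the ten intervention interviews may include few or no non-submitters, although reasons for non-compliance are a stated outcome

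*Protocol*

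**What the plan says.** Section 3.1 of the protocol lists this as a secondary outcome: "More detailed discussion about reasons for compliance/non-compliance with the ISLA platform will be explored in the staff surveys and interviews", and in the surveys and interviews of intervention-group patients. Section 11.2.3 repeats it. Section 8.4 gives the purpose: "We want to document non-compliance as part of this feasibility study to inform a definitive study".

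The number of interviews is in section 7.7: "Ten interviews with patients from each of the two groups and ten interviews with staff". Sections 4 and 7.6 give the same patient numbers and say nothing about selection. The only selection rule is in the Trial Summary, under Trial Design: "Purposive sampling to include a range of ages, sex, ethnicities, physical abilities/carer dependence and socioeconomic status".

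On mode, section 7.7 states: "All interviews will take place via Microsoft Teams and will be digitally recorded with the permission of the participant". Section 7.6 agrees: "the interviews will be conducted via Teams and recorded using digital audio recording". No other mode is offered. Consent for the interviews is also remote: it is recorded, and only the researcher signs the form.

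The intervention arm has 60 patients. Section 8.0 says: "We plan to recruit 120 patients of which 60 will receive monitoring through Isla".

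**The concern.** The characteristic that defines the question, whether a patient sent images, does not steer who is asked about it. The listed characteristics are demographic, functional and socioeconomic. Some of them may correlate with difficulty in using a phone, but none identifies a patient who did not respond to Isla.

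The interview mode may add to this. A patient who sent nothing because of trouble with the device, the connection or the camera may also be harder to bring to an online meeting. The survey has a paper option on request (section 10.0); the interview has no non-digital option.

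Adherence is one of the three progression criteria in section 11.2.2. If it falls short, the designers of the definitive trial will want to hear from people who did not submit. If the ten interviews hold few or none of them, what the interviews say about burden, self-efficacy and barriers comes mainly from people for whom the platform worked.

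**Working it through.** **Inputs from the protocol.** Intervention arm N = 60 (section 8.0); intervention-group interviews n = 10 (section 7.7); adherence thresholds of 40% and 80% (section 11.2.2). A patient is adherent with one photo and a completed questionnaire within 30 days. I treat each non-adherent patient as a non-submitter, so K = 60 × (1 − adherence).

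**The plan's own figure.** Section 11.1 gives a 95% interval of 37% to 63% for 30 adherent patients out of 60. The exact (Clopper-Pearson) interval is 36.8% to 63.2%. The simple approximation is 0.5 ± 1.96 × √(0.25/60) = 0.5 ± 0.127, or 37.3% to 62.7%. The figure reproduces, and this point does not touch it.

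**Selection without regard to submission.** The number of non-submitters among the ten is hypergeometric, with mean 10K/60 and

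P(none) = C(60 − K, 10) / C(60, 10).

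| Adherence | K | Expected among 10 | P(none) | P(at most one) |
|---|---|---|---|---|
| 95% | 3 | 0.5 | 57.3% | 93.1% |
| 90% | 6 | 1.0 | 31.7% | 74.1% |
| 80% | 12 | 2.0 | 8.7% | 35.4% |
| 70% | 18 | 3.0 | 2.0% | 12.6% |
| 60% | 24 | 4.0 | 0.3% | 3.3% |
| 40% | 36 | 6.0 | <0.01% | 0.07% |

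For example, at 95% P(none) = (50 × 49 × 48)/(60 × 59 × 58) = 117,600/205,320 = 0.573.

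**Non-submitters less willing to take part (assumption; the protocol gives no figure).** Let each non-submitter be w times as likely as a submitter to be taken at each successive draw (Wallenius non-central hypergeometric). Then

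P(none) = product over i = 0 to 9 of (60 − K − i) / (60 − K − i + wK).

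- 80% adherence, w = 1/2 (wK = 6): C(48, 10)/C(54, 10) = 27.3%.
- 80% adherence, w = 1/4 (wK = 3): C(48, 10)/C(51, 10) = (41 × 40 × 39)/(51 × 50 × 49) = 63,960/124,950 = 51.2%.
- 60% adherence, w = 1/2 (wK = 12): C(36, 10)/C(48, 10) = 3.9%.
- 60% adherence, w = 1/4 (wK = 6): C(36, 10)/C(42, 10) = 17.3%.

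An interview sample without non-submitters is therefore a real possibility at high adherence or with unequal willingness. It is improbable at middling adherence with equal willingness.

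**The case against.** The strongest reply is that the harm is smallest where it would matter most. A reader might infer that, if adherence lands in the middle progression band (40% to below 80%), the trial will have little evidence on what to change. The figures do not support that. At equal willingness, 60% adherence gives about four non-submitters in ten and a 0.3% chance of none. Only a marked, assumed reluctance among non-submitters changes this. Non-submitters are scarce mainly when adherence is high, and then their absence weighs less on the progression decision. This part of the objection stands.

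It also stands that interviews are not the only source. The day-30 survey goes to all patients, with paper copies on request (sections 7.6 and 10.0). Study teams are to use Isla's view of missed requests partly to understand non-compliance (section 8.4). Patients who do not respond to image requests may be telephoned up to three times (section 7.8), and every patient is called at days 30 and 60 (section 7.6). Patients who answered some requests can also explain missed ones, and the calculation ignores them.

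The calculation treats selection as blind to submission, whereas the protocol specifies purposive sampling. The listed characteristics may bring in some people with digital difficulty, and the list is not stated to be exhaustive. This limits the precision of the percentages. It does not close the gap, because nothing asks for a non-submitter.

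Three further readings are tempting but unsupported:

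- That the interviews are video calls: the text says Teams with audio recording.
- That Teams shuts non-submitters out: section 6.1 provides for a patient's, carer's or study-supplied smartphone or internet access, so Teams at most makes them harder to reach.
- That only survey completers are interviewed: the Trial Summary says interviews take up issues raised in surveys, which describes topics and not selection.

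**Conclusion.** The point holds as a modest gap in the qualitative component. The protocol names interviews as a source of reasons for non-compliance, omits submission status from the sampling characteristics, and offers one digital mode. The ten intervention interviews may therefore include few or no non-submitters. With selection blind to submission, the chance of none is about 9% at the 80% threshold, 32% at 90% and 57% at 95%, and negligible at 60% and below. At 80% it rises to about 27% or 51% if non-submitters are half or a quarter as likely to take part; those ratios are assumptions.

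A reader might go further and infer that acceptability will look better than it is. The protocol does not support that: acceptability also rests on surveys, and unequal participation is plausible but not shown. The interview findings may be skewed towards users. The adherence estimate and its interval are unaffected, and no figure in the protocol is wrong on this account.

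**What to change.** In the Trial Summary and section 7.7, add Isla submission status (none, some or all requests) to the purposive sampling characteristics for the ten intervention-group interviews. State the aim of including non-submitters and partial submitters as far as such patients exist and agree, and identify them from the missed-request view in section 8.4. A fixed quota is not advisable: at 95% adherence there would be only three non-adherent patients in the arm.

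In sections 7.6 and 7.7, change the interview mode to Microsoft Teams or telephone. Keep the present arrangement of recorded consent signed by the researcher, and confirm that it can be followed by telephone.

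The number of interviews stays the same and no new staff are needed. The cost is more contact attempts, fewer interviews with full users, and a change of wording that goes to the sponsor under section 13.8.

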1. BACKGROUND

Over 10 million surgical operations are performed in England annually with approximately 2.1 million having problems with wound healing, of which 500,000 lead to infection.¹ Most of these wound problems happen after patients have been discharged from hospital and they need to be identified and treated early.² Any delay in treating a wound can allow the problem to worsen making it harder to treat.

Digital remote surgical wound monitoring is beginning to be used to monitor patients' surgical wounds at home after they have been discharged from hospital.³ With digital monitoring, patients upload images of their wound and some information using their smartphone in response to pre-programmed text messages.⁴ This offers regular assessment during the time when wound problems are most likely to develop. Following clinician review of images submitted, patients will receive a text to say their wound does not appear to have any problems or they may be contacted for further assessment or treatment. The digital monitoring platform we developed is called Isla and is used in eight cardiac surgery centres in England. To date, over 7,000 patients have submitted 50,000 images. Early evaluations of digital wound monitoring suggest it improves clinical outcomes and has high patient satisfaction; however, it creates a new additional workload for clinicians.⁴

The study will assess a new component for a digital wound monitoring platform. The new component uses artificial intelligence to identify 'red flags' on the images patients submit to the wound monitoring platform. Criteria for priority review (red flags) are:

- Unexpected tissue (deeper than the skin) and/or fluid in the surgical wound
- Abnormal redness/discolouration of the skin spreading from the wound
- Removable stitches or surgical clips detected more than 14 days after surgery
- Incisional Separation

Images that are identified as having a possible red flag are then identified for urgent priority review. This helps clinicians manage this new workload by allowing the most urgent cases to be reviewed first.

The new wound prioritisation module has been developed and has been validated for predictivity, sensitivity and specificity, and inter-rater reliability.

We will conduct a feasibility study of our new AI module with 120 heart surgery patients at two hospitals. Each patient will be randomly allocated to receive the platform with the new detection and prioritising module (for up to 30 days after surgery) plus standard post operative wound care or standard post operative wound care only. Assessment through survey, interviews and platform review is at 30 days and through medical notes review, patient log and patient phone calls at 60 days. Outcomes will assess safety, acceptability, feasibility and health economic assessment.

2. **RATIONALE**

Remote wound monitoring enables clinicians to review patients' surgical wounds regularly and quickly, however the volume of images creates a new workload problem.

With a remote wound platform patients upload images of their wounds to clinicians for review. These new platforms are good for patients as wound problems can be detected and treated early. However, the success of continuous wound monitoring creates a new and increasing workload for staff as it is scaled for (potentially) millions of surgeries annually with multiple images per patient.

This feasibility study assesses a surgical wound monitoring platform that uses artificial intelligence (AI) to assist clinicians to review patients' wounds by prioritising concerning images for urgent action. This will manage staff time more effectively and expedite treatment.

The validated AI module will be assessed in a feasibility study looking at patient safety and patient and staff acceptability outcomes.

